and other cancers), local toxicity/morbidity, cost-effectiveness and quality of life.

Separate sub-protocols, not included in this protocol, will address other endpoints, including cosmetic

outcome, cardiopulmonary toxicity, patient satisfaction and patient preference. These sub-protocols

will be subject to their own sponsorship and regulatory reviews.

TARGIT B Protocol IRAS No: 77045 Version 6.0, Dated 10/09/2018 8. Study design

Core Protocol: This pragmatic, parallel group, superiority randomised trial is designed to directly

compare the outcome, primarily in terms of local control, of two approaches of adjuvant radiotherapy.

Patients selected for breast-conserving surgery who are considered to have a high risk of local

recurrence are eligible to participate in the trial once they have received information and given their

consent.

Individual centres may choose to recruit only a subset of patients eligible as per the entry and

management criteria given in the protocol; for example some centres may decide not to enter patients

who require a second procedure solely to give the TARGIT-boost. These policies are to be

documented in advance and all trial patients treated according to this pre-declared policy. The study

will be analysed under an 'intention to treat policy' (ITT) with stratified analyses performed.

This trial allows entry of patients who are suitable, (or have been rendered suitable by neoadjuvant

systemic therapy) to be treated by breast conserving therapy and who are expected to have a high risk

of local recurrence, (young age, grade III histology, lymphovascular invasion, grossly involved

axillary nodes, etc.), or risk of recurrence in other quadrants of the breast such as extensive intraduct

component (EIC) or lobular carcinoma. Preferably, tumours should not be more than 4 cm in size, as

the largest applicator size is 5cm. Patient consent is sought and randomisation is carried out prior to

the surgical removal of the tumour. After wide local excision of the tumour, a tumour bed boost is

delivered using the Intrabeam system as described previously in the patients who are randomised to

TARGIT Boost. Those randomised to EBRT boost will have this boost delivered by conventional

External Beam Radiation Therapy (EBRT).

Most patients who require treatment for a metachronous breast cancer are excluded from entry to

trials of local treatment. Although there are good reasons for this, later development of recurrence

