cannot be ascribed to the first or second breast tumour for instance, they do need to be treated and

intraoperative treatment may be particularly suitable. The trial will only assess these patients for

ipsilateral local control and their data will be censored for other endpoint assessments.

Changes to protocol

Protocol v2.0 included entry into the trial after the initial surgery was performed. However, at the

first trial steering committee meeting it was decided that this mode of entry was not desirable and

should be removed from the protocol based on the findings of the TARGIT-A trial – which found

that when given as a delayed procedure, TARGIT does not appear to be as effective as when it is

given concurrently with lumpectomy ¹⁵. It has also been found that progesterone receptor status

predicts the response to radiation. Therefore, there will be no stratification as per timing of

TARGIT B Protocol IRAS No: 77045 randomisation with respect to lumpectomy ¹⁵. Instead, we shall stratify as per hormone receptor status (see Table) ¹⁶. This is based on the finding in the TARGIT-A trial that progesterone receptor status appears to be the only factor that predicts the efficacy of TARGIT. The eligibility criteria will also be simplified as it will not include positive margin at first excision as an entry criterion. Therefore, randomisation will be stratified according to participating site as well as by the hormone receptor status. These changes have been incorporated into Protocol v3.0.

Protocol v4.0 included that a 'minimum' of Five "pilot" cases (non-randomised patients suitable to receive TARGIT) will be performed followed by an audit by a member of the Steering Committee (or an appointed delegate). Also, patients will be issued with a participant card so that patients can provide this card whenever they are asked about what type or how much radiation treatment they have received.

Stratification by hormone receptor status

		Tumour ER status					
		ER	ER	ER			
		positive	negative	unknown*			
Tumoum DoD	PgR positive	Stratum 1	Stratum 4	Stratum 0			
Tumour PgR	PgR negative	Stratum 2	Stratum 4	Stratum 0			
status	PgR unknown	Stratum 3	Stratum 4	Stratum 0			

Stratum 0: ER unknown

[figure not shown]
Stratum 1: ER positive, PgR positive
Stratum 2: ER positive, PgR negative
Stratum 3: ER positive, PgR unknown
Stratum 4: ER negative, (any PgR status)

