11.2. Use within the trial

Patients with positive margins: If final pathology shows involved or close margins (evidence of

invasive or in situ tumour at, or within 1mm, of an excision margin or 'ink-on-margin' as per local

practice and multidisciplinary team discussion) re-excision is strongly recommended. In some cases,

this may necessitate a mastectomy. Decision about re-excision or mastectomy should not be

influenced by whether the patient had received TARGIT-Boost or not. For patients who have already

received TARGIT, such re-excision to clear margins should be followed by external beam

radiotherapy excluding the boost. Intraoperative radiotherapy or EBRT boost of the re-excised tumour

bed which had previously received TARGIT should not be done because we have had no experience

regarding its safety.

The procedure for delivering the TARGIT is described below, including the administration of a

prophylactic antibiotic just after the induction of anaesthesia. In this group of patients, special care

should be taken to ensure the wound closure is meticulous, air- and water-tight and sutures are not

removed for at least 2 weeks. If an absorbable suture is used it should be at least 3-0 in thickness,

should not be absorbable within 2 weeks and Steristrips should be used and left in situ for 2 weeks.

Also, in this group the antibiotic cover should be for 5 days.

Pathological Examination: Data from pathological examinations should be recorded on the

appropriate data collection forms and all reporting of pathological findings are to be in accordance

with the TNM Classification.

Radiotherapy

TARGeted Intra-operative radioTherapy (TARGIT): The technique of the operation and the delivery

of radiotherapy have been described in a video available from the TARGIT Trial Operations Office

and at http://www.youtube.com/watch?v=GVlHGpvRf8A. We have established a standard training

protocol before any centre is allowed to recruit into the trial. We shall ensure that the doses are

standardized between all centres.

Preparation of the Intrabeam: TARGIT will either be delivered in the operating theatre immediately

after the removal of the tumour or as a subsequent procedure, a short time later. The procedure has

been described in detail ^{8 9 18}. The device and the arm of the stand are wrapped in a sterile clear plastic

cover. The individual applicators are sterilised prior to the theatre session. The size of the sphere is

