15.2. Statistical analysis

Planned Statistical Analysis: The primary endpoint is the incidence of local recurrence. All comparison will be done on an "intent to treat" basis where all randomised patients will be included in the statistical analysis. Between-treatment group comparisons of proportion of local recurrence will be compared using simple Chi-squared test. Kaplan-Meier curves and log-rank test will be used to compare the time to local recurrence in the two treatment arms. Proportional Hazard regression models will control for possible confounding variables when comparing local recurrence in the treatment groups. We will report 95% confidence intervals for all reported proportions and hazard ratios.

Interim Analysis: Interim analyses will be carried out when 41 events occur or at a median follow up of 3 years, whichever is earlier. We have chosen 3 years because it will include the peak of hazard of local recurrence. This analysis will include the assessment for the need to change the sample size, as well as futility analysis about the continuation of the trial.

In addition, analysis of data will be carried out regularly by the DMC as per MRC guidelines.

Handling of loss to follow up or missing data: In order to carry out an Intent To Treat (ITT) analysis and avoid potential bias resulting from missing data, multiple imputation methods will be used after the missingness mechanisms are established. A full report of the patterns of missing data will be reported based on the recent CONSORT guidelines²⁹. Sensitivity analysis will be carried out and reported.

Planned subgroup analyses: This will include immediate vs. delayed boost (as a second procedure), pre- vs post- menopausal chemotherapy vs. no chemotherapy, neo-adjuvant vs. other, ER, PgR, HER2 status, Oncotype DX score. Further factors will be decided before unblinding of the data.

16. Compliance and withdrawal

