The main ethical issue is the necessity of an additional procedure that would be required in those

patients who are found to be suitable for the trial after their primary operation has already been

performed, and who would otherwise not need a second operation. These patients would be at much

higher risk of local recurrence even after routine radiotherapy (about 15-20%) and thus could

potentially derive significant benefit from TARGIT-boost. The consenting physician/surgeon will

carry out careful discussions about the risk of a second operation (which may not be significant in

these patients who would usually be young and fit) vs. the possibility of a superior result and decision

TARGIT B Protocol IRAS No: 77045 to enrol will be taken on an individual patient basis. We expect that these will constitute about 90 to

120 cases out of the total accrual of 1796.

Research Governance

The sponsor for this clinical trial is UCL. The overall research governance of the trial is determined

largely by the sponsor, including Standard Operating Procedures and Data Protection.

Each centre takes responsibility for the collection and management of its own data. Randomisation

is performed centrally though the TARGIT Trial Operations Office based in London which is also

responsible for the administration of the trial database. Access to the entire dataset is restricted to

designated trials staff and the Trial Statistician. Regular electronic reports will be produced and

passed to each centre for audit and checking purposes. This not only allows each centre to have full

responsibility for its own data, but also ensures there is adequate backup and central auditing of the

data. Standard operating procedures are in place for any data management or clinical queries.

The project is managed by a 4-tiered approach: quarterly meetings of the Trial Steering Committee;

biannual meetings of the Data Monitoring Committee; monthly meetings of the Trial Operations

Group; and weekly meetings of operational staff in the Trial Operations Office. The Trial Operations

Group is responsible for the project management and consists of seven members who are all co-

applicants of this grant. The Trial Steering Committee's role will be overarching as they are the

custodian of the data. The Trial Operations Office is based at UCL and the finances are managed by

the University finance office, which ensures propriety.

Data Monitoring Committee (DMC)

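### Section 18 still expects 90 to 120 patients to enter after their primary operation, although section 8 randomises everyone before tumour removal; the immediate-versus-delayed boost subgroup then has no randomised comparator

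*Protocol*

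**What the plan says.** **Entry rule.** Protocol section 8 (Study design): "Patient consent is sought and randomisation is carried out prior to" the surgical removal of the tumour. Under Changes to protocol in the same section, entry after the initial surgery is described as a feature of version 2.0. At the "first trial steering committee meeting it was decided that this mode of entry was not desirable and" it "should be removed from the protocol based on the findings of the TARGIT-A trial", in which TARGIT given as a delayed procedure appeared less effective than TARGIT given with lumpectomy. The text continues: "Therefore, there will be no stratification as per timing of" randomisation relative to lumpectomy. Section 12 accordingly stratifies by centre and receptor stratum only.

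**Text that still assumes late entry.** Section 18 (Risks and benefits) names as the main ethical issue an extra operation for "patients who are found to be suitable for the trial after their primary operation has already been" performed. It describes how they will be counselled, puts their recurrence risk after routine radiotherapy at about 15-20%, and expects about 90 to "120 cases out of the total accrual of 1796". Section 8 also lets a centre decline patients who would need a second procedure only for the TARGIT boost, which implies that other centres may take them.

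**Delivery.** Section 11.2 allows TARGIT immediately "after the removal of the tumour or as a subsequent procedure, a short time later".

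**Analysis.** Section 15.2, on planned subgroups: "This will include immediate vs. delayed boost (as a second procedure").

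**The concern.** Who may be randomised, and when, is a protocol decision, and version 6.0 gives two answers. Someone reading section 8 concludes that entry after surgery is closed. Someone reading section 18, for example an ethics committee, concludes that it is open and that about one patient in 15 to 20 will come in that way.

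The subgroup follows from the same unresolved point. It is worded by how the boost was delivered. The EBRT boost is given by external beam after surgery and is never an immediate or second surgical procedure, so the classification does not apply to control patients. A between-arm comparison within each level would need a comparator that the wording does not supply.

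**Working it through.** **1. The two readings**

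| | Entry after surgery closed (section 8) | Entry after surgery open (section 18) |
|---|---|---|
| 90 to 120 patients expected | cannot occur | 5.0 to 6.7% of accrual |
| Delayed boost | arises after randomisation, TARGIT arm only | could be recast as timing of entry, known before randomisation in both arms |
| Subgroup as worded | no randomised comparator | not defined by timing of entry |
| Effect on power | none from late entrants, unless the 1796 counts on them | depends on the effect of TARGIT in late entrants, not stated |

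The missing comparator and the power question belong to different columns and should not be added together.

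**2. Share of accrual.** 90/1796 = 5.0%; 120/1796 = 6.7%.

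**3. The plan's own sample size (section 15.1).** Inputs: 5.64% against 2.9%, two-sided alpha 0.05, power 80%. The formula for two proportions, with pooled variance under the null and no continuity correction, is

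n per arm = [1.96·√(2p̄(1−p̄)) + 0.842·√(p1(1−p1) + p2(1−p2))]² / (p1−p2)²

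This gives 854 per arm, 1708 in total, against 1707 stated. At 853.5 per arm, power is 80.0%. The stated figure reproduces.

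**4. Power if late entrants are included.** Let f be their share, r their control-arm risk (15% or 20%, section 18) and k their risk ratio. Assume equal allocation, 853.5 evaluable per arm, and that 5.64% and 2.9% describe the other patients.

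- Control rate = (1−f)·5.64% + f·r
- TARGIT rate = (1−f)·2.9% + f·r·k

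Example: f = 0.050, r = 15%, k = 1 gives 6.11% against 3.51% and power 71.0%.

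| f | r | No gain (k = 1) | 25% reduction (k = 0.75) | Planned ratio (k = 2.9/5.64 = 0.514) |
|---|---|---|---|---|
| 0.050 | 15% | 71.0% | 77.7% | 83.2% |
| 0.050 | 20% | 68.9% | 77.7% | 84.7% |
| 0.067 | 15% | 68.0% | 77.0% | 84.2% |
| 0.067 | 20% | 65.3% | 77.1% | 86.1% |

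The values of k are assumptions; the protocol gives none for this group. With the planned ratio, power rises because the high-risk patients add events.

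**5. Power if they are excluded and not replaced.** 1796 − 90 = 1706 and 1796 − 120 = 1676. After 5% attrition these are 1621 and 1592, with power 77.9% and 77.2%. If they are replaced, the planned power is unchanged.

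**The case against.** **Stale wording.** Section 18 reads like text left over from version 2.0. Central staff confirm eligibility before randomising (section 12), so sites do not act on their own reading. That makes actual enrolment by the wrong route less likely. It does not remove the contradiction, which lies between the design text of section 8 and the current text of section 18 and stands without the change history.

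**Later delivery is not later entry.** This stands. A patient randomised before lumpectomy can still receive TARGIT in a subsequent procedure, so section 11.2 does not by itself contradict section 8. It only needs to say which case it covers.

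**The subgroup is secondary and its detail may sit in an analysis plan.** That is fair for details such as the model or the test. But the protocol itself names the factor, and names it by mode of delivery. It is also true that a subgroup based on a pre-randomisation factor gives a randomised comparison without being a stratification factor, so stratification by timing is optional.

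**Dilution of power.** A reader might infer that late entrants cut power to 65-71%. The documents do not support this. Section 8 says only that delayed TARGIT appeared less effective in TARGIT-A, which section 6 describes as testing TARGIT as the only radiotherapy in patients at low risk; it does not say that a delayed boost gives no gain. Section 18 expects that these patients could benefit. Over the plausible range, even the direction of the change is open.

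**Conclusion.** The point holds as an inconsistency in current protocol text and a badly fixed subgroup. Section 8 (randomisation before tumour removal, late entry withdrawn, no stratification by timing) and section 18 (90 to 120 late entrants, 5.0 to 6.7% of 1796) cannot both be right. Under section 8, the immediate-versus-delayed subgroup has no randomised comparator, because its levels exist only in the TARGIT arm and are known only after randomisation.

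No power loss is established. Power is about 65-71% with no gain, about 77-78% with a 25% reduction and about 83-86% with the planned relative effect, if the 15-20% risk comes on top of the 5.64% assumed for the other patients. It is about 77-78% if these patients are excluded and not replaced. The sample size calculation reproduces and is not itself in error. Which entry rule is clinically right is not judged here.

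**What to change.** Reconcile sections 8, 15.2 and 18 to a single entry rule; the choice is the sponsor's. In section 8, bring the sentence on patients who need a second procedure only for the boost into line with that rule. In section 11.2, state whether a subsequent procedure refers to delivery only.

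- **If late entry is closed:** delete the 90 to 120 estimate and the related text in section 18. Remove immediate versus delayed boost from the between-arm subgroups, or label it a descriptive, non-randomised comparison within the TARGIT arm.
- **If late entry is open:** correct section 8. Define the subgroup by timing of randomisation relative to surgery, recorded before randomisation in both arms; stratification is optional. State in section 15.1 the risk and effect assumed for these patients and the resulting power.

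The cost is amendment wording. No extra patients are needed for the reconciliation itself. If late entry is open, the restated power will show whether the sample size needs to change.
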